Treatment failure will be defined as any crossover from one treatment to another due to patient's respiratory distress and discomfort. To be more specific, switch of gas flow from 40L/min to 60L/min, crossover from either NHF group to standard practice (Venturi mask) or need for more advanced respiratory support such as non-invasive ventilation or invasive mechanical ventilation, inability to reverse FiO_2 and/or gas flow escalation above initial settings within 48 hours of its initiation. Escalation reversal will be defined as return to initial (or lower) FiO_2 and/or gas flow for ≥ 4 hours.

Inclusion criteria will be: Cardiac ICU adult patients > 18 years after elective or urgent cardiac surgery having passed a successful Spontaneous Breathing Trial (SBT) with T-piece and $\text{FiO}_2=0.6$. A successful SBT will have to fulfil the following criteria^{31, 32, 33} respiratory rate: 12-29 breaths/min, $\text{SpO}_2 > 92\%$, $\text{PaCO}_2 < 45\text{ mmHg}$, heart rate <120/min, and systolic arterial pressure of 90-160 mmHg while receiving norepinephrine at a rate of 0.00 $\mu\text{g}/\text{kg}/\text{min}$ to 0.15 $\mu\text{g}/\text{kg}/\text{min}$. The most important inclusion criterion is residual respiratory impairment at the end of SBT defined as $\text{PaO}_2/\text{FiO}_2 < 200 \text{ mmHg}$ while receiving $\text{FiO}_2=0.6$. The decision to extubate under these specific conditions will be made by the attending physicians.

The exclusion criteria will comprise: 1) Obstructive Sleep Apnea Syndrome supported by a continuous positive airways pressure device, 2) preoperative diagnosis of Chronic Obstructive Pulmonary disease, 3) patients already tracheostomized, 4) do not resuscitate status, 5) Glasgow Coma Scale score <13, 6) Insufficient knowledge of Greek Language , and 7) any visual or hearing impairment.

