Following extubation, patients will be randomly assigned to Study group 1 or 2, or to Control group at 1:1:1 ratio. Blocks of 3 numbers will be consecutively drawn from a sequence of 99 unique random numbers (range, 1-99). Random numbers will be generated by using Research Randomizer version 4.0 (www.randomizer.org). Upon patient enrollment, attending investigators will receive text message on their mobile phone devices. The text message will display the patient's code number and group.

Patient monitoring and data collection

Continuous patient monitoring will include electrocardiographic lead II, intra-arterial pressure, SpO₂, and respiratory rate.

Data on patient characteristics, including the European System for Cardiac Operative Risk Evaluation (EUROSCORE) II will be collected at baseline. Data collection time points for SpO₂, respiratory rate, PaO₂/FiO₂, comfort with respect to dyspnea and respiratory support modality (VAS score^{34,35,36}), accessory muscles' use, arterial pressure and heart rate, vasopressor support, and core body temperature will be as follows: within 30 min of extubation (baseline) and at 1, 2, and 4 hours, and every 4 hours onwards until 48 hours postextubation. Fluid balance of the first 24 and 48 hours postextubation will be recorded as well.

Adverse events/clinical course complications (e.g. hypoxemia and/or need for re-intubation, arrhythmias such as atrial fibrillation, occurrence of delirium,^{37,38,39,40,41} epileptic seizures, surgical re-exploration due to bleeding, ICU readmission, chest wound infection), and any patient discomfort/intolerance related to HFNC will also be recorded.

Management of respiratory support

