Patients will be assessed for gradual reduction in the intensity of respiratory support or need for support escalation every 4 hours postextubation. Gradual weaning from NHF will be accomplished by FiO₂ decrease to 0.5, followed by gas flow decrease to 30 L/min NHF weaning target will include an FiO₂ of 0.4 and a gas flow of 20 L/min.^{8,42} If at an NHF FiO₂ of 0.4 and a flow rate of 20 L/min, SpO₂ can be maintained at >92% and respiratory rate remains within 12-20 breaths/min for ≥ 2 hours, patients will be switched to a Venturi mask providing an FiO₂ of 0.4). In the Control group, a reduction of FiO₂ to 0.4 (via a Venturi mask) will be sought. Patients of all groups fulfilling the aforementioned SpO₂/respiratory rate criteria for at least 4 hours while receiving an FiO₂ of 0.4 via a Venturi mask will be considered for ICU discharge. As part of standard practice, patients will be scheduled for twice-daily physiotherapy.

Regarding treatment escalation in Study groups, if SpO₂ drops to $\leq 92\%$ for at least 5 min at a gas flow of less than 60 L/min, gas flow will first be increased by 5-10 L/min.⁴ Next, if SpO₂ remains at or below 92%, FiO₂ will be increased⁴³ to achieve an SpO₂ of >92%. In the Control group, an SpO₂ of 92% or less for at least 5 min will be initially treated with FiO₂ increase. In all groups, persistent and/or worsening hypoxemia will be ultimately treated with non-invasive mechanical ventilation and/or reintubation and initiation of invasive mechanical ventilation.

Treatment decisions and premature discontinuation of physiological data collection

Changes in the intensity and/or modality of respiratory support will ultimately be decided by the primary attending physicians of the patients. Initiation of mechanical ventilation or ICU discharge within 48 hours of extubation will result in discontinuation of the pre-specified 4-hourly patient data collection.

Outcome measures

Primary: Occurrence of treatment failure; regarding the NHF groups, this will be further specified as inability of weaning from NHF (i.e. inability of achieving successful weaning from NHF) according to study protocol.

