Secondary: 1] Successful maintenance of an SpO₂ of >92% and a respiratory rate of 12-29 breaths/min at the specified time points of follow-up; the term "successful" corresponds to the absence of any escalation of respiratory support above its initially specified level for each one of the Study groups and the Control group; 2] PaO₂/FiO₂ at the specified time points of follow-up; 3] Any use of accessory respiratory muscles at the specified time points of follow-up; and 4] Patient comfort as regards dyspnea, and patient tolerance of NHF support according to a VAS score.

Additional: 1] Length of cardiothoracic ICU stay; 2] Length of hospital stay; 3] ICU and in-hospital mortality; and 4] Adverse events (e.g. hypoxemia and/or need for re-intubation, arrhythmias such as atrial fibrillation, occurrence of delirium, epileptic seizures, surgical re-exploration due to bleeding, ICU readmission, chest wound infection), and any patient discomfort/intolerance related to NHF.

Sample Size and Power Analysis

The proposed sample size is based on a formal power calculation, i.e. an *apriori* power analysis, which is an efficient method of controlling statistical power before a study is actually conducted; for power analysis, G*Power 3 software was used.⁴⁴ We predict a treatment failure rate of 15% in the 2 Study groups (10% in Study group 1 and 20% in Study group 2) and a failure rate of 51% in the Control group. The predicted NHF-to-control treatment failure ratio of 0.29 corresponds to the lower limit of the 95% confidence interval (CI) of a previously determined "NHF vs. Control" odds ratio for support escalation.²⁵ For alpha=0.05 and power=0.80, 63 patients (n=21 per group) will be required. However, we cannot exclude a potential risk for dropouts and/or missing data. To compensate for such a risk, we propose the ultimate enrolment of 99 patients (i.e. n=33 per group), in order to achieve an alpha value of 0.05, a power of 0.96, and a "safety margin" of 57% as regards possible dropouts and/or missing data. The predicted study enrollment rate is 40-50 patients per year.

Interim Analysis and Data Monitoring

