$\text{SpO}_2 > 92\%$, and respiratory rate within 12- 20 breaths/min will be assessed as binary outcomes (i.e. maintenance vs. no maintenance of SpO_2 /respiratory rate above/within the aforementioned limits without escalation of support above initial level) Logistic regression models will be fitted using group, time, and group*time interaction as explanatory variables. Changes in oxygenation, VAS comfort scale score, and non-outcome follow-up variables (i.e. PaCO_2 , arterial blood lactate, hemoglobin concentration, hemodynamic variables, temperature, and vasopressor support) will be analysed by using linear mixed models analyses with group, time, and group*time, as fixed factors, and "patients" as random factor. Dependent variables with skewed distributions will be log-transformed. The Bonferroni correction will be applied on the P values of pairwise comparisons.

Two-tailed P values will be reported. Statistical significance will be accepted at 0.05. Analyses will be conducted using SPSS version 21 or any subsequent version (IBM corporation, Armonk NY).

Importance of the study

The early use of NHF in post-extubated cardiac surgery patients may potentially assist them in achieving a faster recovery by providing higher and more stable levels of humidified and warmed oxygen while supporting the respiratory effort through positive airway pressures. This could also be associated with a reduction in the risk for postoperative pulmonary complications. This study may also help in determining the best level of initial NHF support in cardiac surgery patients with postoperative hypoxemia.

Study Funding Statement

The AIRVO™ 2 (Fisher & Paykel Healthcare, Auckland New Zealand) device (with built in flow generator) is already available at our institution. Regarding disposables, we estimate a total cost of 90 Euro per patient (heated humidifier, 60 Euro; Nasal prongs, 15 Euro; compatible opti flow circuit, 15 Euro. The maximum cost of disposables is estimated at 5940

Euro (+24% value added tax). This cost will be covered by the Special Account for Research Funds, University of Athens Medical School, Athens, Greece. The current study will not cause any financial burden to Evangelismos Hospital.

Doctoral Thesis

This study corresponds to the Doctoral Thesis of [name].

References (updated 14/09/2018)

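### The repeated SpO2/respiratory-rate outcome is planned as ordinary logistic regression with no allowance for within-patient correlation, so any test that pools a patient's time points rejects too often

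*Combined protocol and SAP*

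**What the plan says.** **Outcome.** Under Outcome measures, secondary outcome 1 is maintenance of SpO2 and respiratory rate at each follow-up time point, where success requires "the absence of any escalation of respiratory support above its initially specified level". The Statistical Analysis Plan repeats the condition: "limits without escalation of support above initial level".

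**Schedule.** Patient monitoring and data collection sets readings "within 30 min of extubation (baseline) and at 1, 2, and 4 hours, and every 4 hours onwards until 48 hours postextubation".

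**Binary model.** The Statistical Analysis Plan states: "Logistic regression models will be fitted using group, time, and group*time interaction as explanatory variables". It mentions no patient term, GEE or robust variance, and does not say how time is coded or which group contrast is tested.

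**Continuous outcomes.** The next sentence specifies "linear mixed models analyses with group, time, and group*time, as fixed factors" and adds patients as a random factor. It covers oxygenation, the comfort score and the non-outcome follow-up variables, not the binary outcome. Bonferroni correction is then applied to pairwise comparisons.

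**Early stopping of readings.** The section on treatment decisions says: "Initiation of mechanical ventilation or ICU discharge within 48 hours of extubation will result in discontinuation of the pre-specified 4-hourly patient data collection".

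**The concern.** Because time is a model term, each patient must contribute several rows. Ordinary logistic regression takes all rows as independent, and with positive within-patient correlation that makes the standard error of a pooled group comparison too small.

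Some correlation is built into the outcome. A patient supported above the initial level is not maintained at that reading, and stays so at later readings until support comes down. The Methods count as treatment failure an inability to reverse FiO2 and/or "gas flow escalation above initial settings within 48 hours of its initiation". Failure is not expected to be rare: "We predict a treatment failure rate of 15% in the 2 Study groups", and 51% in the Control group.

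At stake is a false claim of a group difference in this secondary outcome, tested at two-sided 0.05 in an unblinded trial.

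**Working it through.** **The plan's own figures.** The documents give no figure for this analysis beyond alpha 0.05. The sample size for the primary outcome does reproduce. With failure rates of 10%, 20% and 51%, the mean is 0.27 and w = sqrt{[(0.17² + 0.07² + 0.24²)/3]/(0.27 × 0.73)} = 0.393. A 2-df chi-square test then has power 0.804 at N = 63 and 0.948 at N = 99, against the stated 0.80 and 0.96. A normal-approximation comparison of 15% with 51% at 2:1 gives 0.963 at N = 99. None of this depends on the secondary model.

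**Inputs from the documents.** 33 patients per group. Readings at baseline, 1, 2 and 4 h (4 readings), then 8 to 48 h every 4 h (11 readings): 15 in all, or 495 rows per arm.

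**Assumed.** ICC 0.05 and 0.10, the same correlation between any two readings (exchangeable), and a maintenance rate of 75% or 80% in every arm.

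**Closed form, time-averaged group effect (2 df).** The design effect is D = 1 + (m − 1) × ICC. The 5% critical value is 5.991, half of which is 2.996, so true rejection is exp(−2.996/D).

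| Readings per patient | ICC | D | Rejection |
|---|---|---|---|
| 15 | 0 | 1.0 | 5.0% |
| 15 | 0.05 | 1.7 | 17.2% |
| 15 | 0.10 | 2.4 | 28.7% |
| 7 (series end at 16 h) | 0.05 | 1.3 | 10.0% |
| 7 (series end at 16 h) | 0.10 | 1.6 | 15.4% |

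The 495 rows per arm are worth 495/1.7 = 291 independent readings at ICC 0.05 and 495/2.4 = 206 at 0.10.

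**Bonferroni does not repair this.** With three pairwise time-averaged comparisons, each is tested at 0.05/3 = 1.7% (z = 2.394). True rejection per comparison is 2 × [1 − Φ(2.394/√1.7)] = 6.6% at ICC 0.05 and 2 × [1 − Φ(2.394/√2.4)] = 12.2% at ICC 0.10.

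**Null simulation, complete 15-point series.** Rejection at a nominal 5%:

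| Test | ICC 0.05 | ICC 0.10 |
|---|---|---|
| Time-averaged group effect (linear time centred, or group main effect) | 17-19% | 28-32% |
| Time-averaged group effect, categorical time | 19% | 30% |
| Joint group plus group*time, linear time | 13-14% | 21% |
| Group term, linear time not centred (effect at time zero) | 7-9% | 12% |
| Group term, categorical time, baseline reference | 3% | 3% |
| Group*time, linear time | about 4% | 3-4% |

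The maintenance rate matters little: at ICC 0.10 the centred group test gives 30% at a rate of 60% and 28% at 90%.

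**Other correlation patterns.** Two were tried: autoregressive correlation of 0.3 or 0.5 per 4 h, and persistent failure. The latter assumes 15% failure in every arm, a uniform failure time, no maintenance afterwards and 10-20% chance misses.

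- Centred group test: 24-37% (autoregressive) and 26-41% (persistent failure).
- Group*time with linear time: 25-34% and 11-15%. Stronger serial correlation, at latent values of 0.8 and 0.9 per 4 h, gave 36% and 32%.
- Group*time with categorical time (likelihood ratio): 2-6%, not inflated.
- Three Bonferroni-corrected pairwise contrasts at one time point: 2-3%, not inflated.

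**The case against.** The strongest reply is that the plan may intend a test that is not inflated. The next sentence calls time a fixed factor, which in SPSS usage normally means categorical, and Bonferroni-corrected pairwise comparisons fit that reading. If those comparisons are made at single time points, each uses one row per patient and nothing is inflated. This stands as far as it goes, but the wording belongs to the linear mixed models, the contrast is not stated, and a time-averaged contrast with categorical time is as inflated as with linear time.

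A second reply is that GEE or a mixed logistic model is meant, which SPSS can fit. That is possible, but the text says so only for the continuous outcomes. If it is meant, the remedy is to write it down.

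Third, complete series are unlikely. Readings stop at ventilation or ICU discharge, and discharge is considered after at least 4 hours of meeting the criteria on a Venturi mask at FiO2 0.4. This stands: the shorter-series figures of 10% / 15% belong beside the larger ones. The persistent-failure scenario is also severe, because the protocol allows escalation to be reversed and rows after ventilation exist only if they are scored as not maintained.

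A reader might infer that the group*time test is too liberal whenever correlation decays or failure persists. That does not follow: it holds only for linear time, and under exchangeable correlation even that test is slightly conservative.

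**Conclusion.** The omission is certain: a repeated binary outcome is given a model for independent observations, one sentence before the plan handles the same problem for its continuous outcomes. Tests that pool a patient's readings over-reject under any positive within-patient correlation. The size is conditional. At an assumed ICC of 0.05 / 0.10, the time-averaged group test runs at about 17-19% / 28-32% with complete series and about 10% / 15% with series ending near 16 h. Group*time is inflated (about 11-34% at the moderate correlations tried) only with linear time and serially decaying correlation or persistent failure.

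A reader might go further and conclude that every group test of this outcome is invalid, or that the trial's main result is in doubt. The documents support neither. Single-time-point contrasts keep their level, the coding and contrast that decide the matter are unstated, and the primary Cox analysis and sample size do not use this model. It should be fixed, as a cheap correction to one secondary analysis.

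**What to change.** Replace the sentence with a logistic model that accounts for patient clustering, for example:

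> The binary outcome will be analysed by a GEE logistic model with group, time and group*time, clustered on patient, with small-sample-corrected robust standard errors. Time will be coded as [state], and the group contrast tested will be [state].

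Choices to settle in advance:

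- **Linear time** is one option, but assumes a straight-line trend in the log-odds. If the group term is to be a time-averaged effect, state the centring time. The mean of the full schedule is 315/15 = 21 h, but truncated series will have an earlier mean.
- **Categorical time** is closer to the fixed-factor wording. With 15 levels and few early events, robust errors for a time-averaged contrast were unreliable (30-38% rejection in simulation).
- **A patient random intercept** kept the time-averaged group test at 4-6%, but its linear group*time test rejected 27% under autoregressive correlation of 0.3 per 4 h and 24% under persistent failure.

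**Cost.** A few sentences and no new data. The standard error of the time-averaged group effect grows about 1.3-fold at ICC 0.05 (√1.7) and 1.5-fold at ICC 0.10 (√2.4), so intervals widen and power for this outcome falls. With 99 patients the corrected GEE test is near nominal rather than exact: about 4.5-6% in most scenarios and 8% in the worst. Without the small-sample correction, clustered errors gave about 5-9%.

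Separately, the respiratory-rate limits for this outcome must be reconciled: Outcome measures gives 12-29 breaths/min and the Statistical Analysis Plan gives 12-20.

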Studies applying NHF immediately after extubation in cardiac surgery patients revealed better oxygenation and less need for advanced methods of respiratory support compared to conventional oxygen devices^{25,26}, and similar results compared to noninvasive ventilation²⁷. However, Zochios et al,²⁸ summarized all the available up to date data of NHF compared to conventional oxygen devices and non-invasive ventilation in patients undergoing cardiothoracic surgery and they did not find any further benefit by NHF use. The aforementioned discordant results could be explained by the differences in the studied populations and NHF flow settings. The proposed initial flow rate differs among the studies, with some authors^{2,4} suggesting initial lower flows (35-40 L/min) that will be better tolerated by the patients and others suggesting initial maximal flows (60 L/min) to rapidly relieve dyspnea and prevent muscle fatigue.^{29,30}

Aim

The primary goal of the study is to evaluate the efficacy of NHF versus conventional oxygen systems as regards treatment failure (as defined below) and respiratory parameters [respiratory rate, PaO_2 / (fraction of inspired oxygen) FiO_2 , peripheral oxygen saturation (SpO_2), use of accessory muscles, and dyspnea and comfort as regards the technique of respiratory support by using a visual analogue scale (VAS) after the extubation of cardiac surgery patients. An additional major goal of the study is to compare two different initial NHF flows of 60 L/min and 40 L/min, intensive care unit (ICU) Length of Stay, Hospital Length of Stay, rates of ICU re-admission and re-intubation and any other respiratory / non-respiratory complications and adverse events. The rate of failure of the initial treatment will be determined as the primary study outcome.

Methods

This is a prospective, non-blinded, randomized study in post-extubated cardiac surgery patients. The study population will consist of three patient groups: The first group (Study Group 1) will include patients on NHF with initial settings of $\text{FiO}_2=0.6$ and gas flow=60L/min. The second group (Study Group 2) will include patients on NHF with initial settings of $\text{FiO}_2=0.6$ and gas flow=40L/min. In the third group (control group) all patients will receive oxygen therapy according to the standard practice of our cardiac ICU department, i.e., Venturi mask with $\text{FiO}_2=0.6$ and flow of 15 L/min.

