At 1 year following study start, an interim analysis will be conducted by Drs. [name] (Senior Consultant in Intensive Care Medicine, First Department of Intensive Care Medicine, University National and Kapodistrian University of Athens Medical School, Evangelismos General Hospital, Athens, Greece) and [name] (Senior Consultant, Department of Cardiac Surgery, Evangelismos General Hospital, Athens, Greece). The analysis will be focused at evaluating and confirming 1) the safety of the study protocol (including any reported adverse events); 2) the applicability of the study protocol (including an assessment of the achieved level of adherence to the specified investigational interventions); 3) the completion of the attached study forms as mandated by the study protocol; and 4) the safety of the electronically stored patient data. Actions related to the

aforementioned points 1-4 may be undertaken at the discretion of the aforementioned study-independent Colleagues at any time point throughout the conduct of the current study. Data quality and completeness will also be evaluated by the aforementioned study-independent Colleagues after the completion of the study.

Statistical Analysis Plan

Analyses will be performed according to intention-to-treat principle. Distribution normality will be determined by Kolmogorov Smirnov test. Continuous variables will be presented as mean \pm SD or median (IQR). Qualitative variables will be presented as number (percentage). Percentages will be compared by Fisher's exact test.

The effect of group on treatment failure will be assessed using multivariable Cox regression. Hazard ratios and respective 95% confidence intervals will be determined for group, EuroSCORE II (which includes age and gender as risk factors), body mass index, cardiopulmonary bypass time, and duration of postoperative sedation and pre-extubation assisted and spontaneous breathing.

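### Bonferroni on the pairwise comparisons is valid but inefficient, and its family is undefined; for a single set of three group contrasts a closed test keeps the same error control with more power

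*Combined protocol and SAP*

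**What the plan says.** Methods: "The study population will consist of three patient groups". Under Randomization procedure, "patients will be randomly assigned to Study group 1 or 2, or to Control group at 1:1:1 ratio". There are therefore three possible between-group contrasts.

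The Statistical Analysis Plan analyses treatment failure by multivariable Cox regression. "Hazard ratios and respective 95% confidence intervals will be determined for group" and for the covariates. That paragraph names neither an overall group test nor a pairwise correction. Percentages are to be compared by Fisher's exact test.

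The next paragraph covers the repeated outcomes, using logistic and linear mixed models with group, time and their interaction. It closes with the sentence at issue: "The Bonferroni correction will be applied on the P values of pairwise comparisons". The significance rule follows: "Two-tailed P values will be reported. Statistical significance will be accepted at 0.05".

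Sample Size and Power Analysis assumes "10% in Study group 1 and 20% in Study group 2) and a failure rate of 51% in the Control group", and states: "For alpha=0.05 and power=0.80, 63 patients (n=21 per group) will be required". Enrolment is then raised to 99 (33 per group) for a stated power of 0.96.

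**The concern.** Bonferroni guards against the worst case for any set of comparisons. With three groups and one outcome at one time, that worst case cannot occur. Either all three groups are equal, which a single overall test covers, or at most one pair is truly equal, so at most one false pairwise claim is possible. Dividing 0.05 by three then costs power without tightening the familywise limit.

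The trial's questions are pairwise. The Aim section asks whether nasal high flow beats conventional oxygen, and makes the comparison of 60 with 40 L/min an additional major goal. If the correction reaches treatment failure, the 40 L/min arm has about an even chance of being shown better than control at the plan's own rates.

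The sentence also leaves its family open. It could mean three contrasts per outcome, three at each time point, or all contrasts over time. These lead to different thresholds and different error rates.

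**Working it through.** **Inputs.** Three groups, 1:1:1, 33 per group; failure rates 0.10 (60 L/min), 0.20 (40 L/min) and 0.51 (control); two-sided 0.05; Fisher's exact test. All are from the protocol. Assumption: the family is the three group contrasts on treatment failure, so the Bonferroni threshold is 0.05/3 = 0.0167.

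**The plan's own figures.** Overall chi-square test, 2 degrees of freedom. Mean rate (0.10 + 0.20 + 0.51)/3 = 0.27. Effect size w² = [(0.17² + 0.07² + 0.24²)/3]/(0.27 × 0.73) = 0.0305/0.1971 = 0.155, so w = 0.393. The noncentrality is N·w²: 9.74 at N = 63 and 15.30 at N = 99. Power is 0.804 and 0.948, against the stated 0.80 and 0.96. The sample size is thus consistent with an overall three-group test, which a pairwise correction does not change.

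**Why the closed procedure is valid.** If any two of the three pairwise equalities hold, all three groups are equal. The closed family is therefore the three pairs plus the overall null. A pair may be claimed when its own test and the overall test are both significant at 0.05, and the familywise error is then at most 0.05.

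**Power.** Full enumeration of the 34³ outcomes, with an exact (Freeman-Halton) overall test and Fisher pairwise tests, weighted by the binomial probabilities. Holm compares the ordered P values with 0.05/3, 0.05/2 and 0.05.

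| Claim | Bonferroni | Holm | Closed |
|---|---|---|---|
| 40 L/min vs control | 0.50 | 0.59 | 0.69 |
| 60 L/min vs control | 0.88 | 0.88 | 0.94 |
| 60 vs 40 L/min | 0.05 | 0.08 | 0.12 |
| Both nasal high flow arms beat control | 0.49 | 0.57 | 0.68 |

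Power of the overall test is 0.95. With Pearson tests in place of Fisher (simulation), Bonferroni to closed is 0.61 to 0.78, 0.93 to 0.95, 0.10 to 0.21 and 0.59 to 0.77, in the same order.

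**Error.** On a grid of rates from 0.05 to 0.95, the closed test's familywise error peaks at 0.046 when all rates are equal and 0.036 when one pair is equal. Bonferroni with Fisher tests peaks at 0.025 when all are equal.

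**In patients.** n per group = [z(α/2)·√(2p̄(1−p̄)) + z(0.20)·√(p₁(1−p₁) + p₂(1−p₂))]²/(p₂−p₁)². For 0.20 vs 0.51 and 80% power:
- α = 0.05: (1.960 × 0.6767 + 0.842 × 0.6402)²/0.31² = 36.2, so 37.
- α = 0.0167: (2.394 × 0.6767 + 0.842 × 0.6402)²/0.31² = 48.5, so 49.

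The first figure ignores the small cost of the overall test.

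**Several time points.** Patient monitoring and data collection lists baseline, 1, 2 and 4 hours, then every 4 hours to 48: 4 + 11 = 15 time points, and 15 × 3 = 45 between-group contrasts. Simulation with normal data, 33 per group and assumed within-patient correlation 0.3 to 0.8 gave these familywise errors:
- One joint overall test, then unadjusted pairs at every time point: 40% to 77% if only one time point truly differs; 19% to 46% if both nasal high flow groups differ from control by 1 SD throughout.
- Bonferroni over all 45: at most 5%.
- Bonferroni over three at each time point: 8% to 42% across time points.

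**Intervals.** A pair can have raw P below 0.05 when the overall test fails. This happens for at least one pair in 1.1% of trials at the plan's rates, and in 4% to 8% under smaller assumed effects (for example 20/20/45% or 20/35/45%).

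**The case against.** The strongest reply is about scope. The Bonferroni sentence closes the paragraph on the repeated-measures models, and treatment failure is handled in the paragraph before it with no correction named. The power figures above are for treatment failure, so if the sentence stops at its own paragraph these losses do not arise in the Cox analysis. This stands, and it is why the figures are conditional. It also shows that the sentence needs a stated family.

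A reader might infer that every pairwise P value is multiplied by three. The documents do not say so; with 15 time points the family could be as large as 45 contrasts, or could include changes within groups.

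A reader might also infer that the corrected P values will contradict the 95% intervals for the hazard ratios. That needs Bonferroni to be applied to those hazard ratios, which the plan does not clearly say.

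Finally, Bonferroni is valid, needs no preceding test and has matching simultaneous intervals, which the closed procedure lacks. That is a real advantage. Against it, Holm rejects everything Bonferroni rejects at the same familywise error, for any family and with no preceding test.

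**Conclusion.** The point holds as one of efficiency and definition. The plan contains no statistical error here, and the correction does not undermine its stated sample size.

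For a single family of three contrasts, the closed procedure gains 18 points for 40 L/min versus control (0.505 to 0.688) and 19 for both arms beating control (0.485 to 0.677). It gains 6 points each for 60 L/min versus control and for 60 versus 40 L/min, and the latter stays badly underpowered at 0.12 (0.21 with Pearson tests). The gain is therefore concentrated in the claims that involve the 40 L/min arm and control.

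The size rests on the plan's predicted rates, 33 evaluable patients per arm, and binary tests. It does not describe the Cox model: the documents give no event-time distribution or covariate effects, so Cox power could only be simulated on assumed event times, and no such figure is used here.

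It would be tempting to conclude that three groups never need a correction. That is true only within one three-contrast family. Across time points a correction is still needed, and one overall test per outcome would not replace it.

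**What to change.** Replace the Bonferroni sentence with text that does three things:

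1. **Define the family** for each outcome, and say whether treatment failure is covered.
2. **Single three-contrast families** (treatment failure, and any other outcome compared once): test the three groups overall at two-sided 0.05. If significant, test each of the three pairs at two-sided 0.05. If not, claim no pairwise difference. For the Cox analysis the overall test is the two-degree-of-freedom test of group.
3. **Comparisons at several time points:** correct over the whole stated family, using Holm in place of Bonferroni. Do not use one joint overall test followed by unadjusted pairs at every time point.

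If the sponsor prefers adjusted P values throughout, Holm alone is the simpler option (0.59 for 40 L/min versus control).

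The cost is a few lines in the analysis plan and no extra patients or data. The drawbacks should be stated there: pairwise claims in the single families depend on the overall test (power 0.95 at the plan's rates), the 95% intervals are not simultaneous, and an interval can still exclude no effect when the overall test fails (about 1% of trials at the plan's rates).
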